DNA Analysis. The analysis of blood for genetic research raises special issues of confidentiality. Variation in some genes is known to be directly related to risk for certain illnesses. In some cases, knowledge of genetic information could have negative psychological consequences or could affect access to or retention of certain benefits or entitlements. For example, the information could potentially be used against an individual if it were revealed to insurance companies or potential employers. We will take precautions to ensure that confidentiality is maintained and that the genetic information is not unintentionally disclosed to inappropriate third parties.

12. Data and Safety Monitoring Plan: Include an appropriate Data and Safety Monitoring Plan (DSMP) based on the investigator's risk assessment stated below. (Note: the HIC will make the final determination of the risk to subjects.)

- a. What is the investigator's assessment of the overall risk level for subjects participating in this study? **GREATER THAN MINIMAL RISK**
- b. If children are involved, what is the investigator's assessment of the overall risk level for the children participating in this study? presenting a minor increment over minimal risk with no prospect of direct benefit to individual subjects, but likely to yield generalizable knowledge about the subject's disorder or condition (per 45 CFR § 46.406), with permission obtained from both parents.
- c. Include an appropriate Data and Safety Monitoring Plan. Examples of DSMPs are available here <http://your.yale.edu/policies-procedures/forms/420-fr-01-data-and-safetymonitoring-plans-templates> for
 - i. Included at the end of the document.
- d. For multi-site studies for which the Yale PI serves as the lead investigator:
 - i. How will adverse events and unanticipated problems involving risks to subjects or others be reported, reviewed and managed? *Write here*
 - ii. What provisions are in place for management of interim results? *Write here*
 - iii. What will the multi-site process be for protocol modifications? *Write here*

13. Statistical Considerations: Describe the statistical analyses that support the study design.
Statistical Plan for aims 1 and 2. Justification of Sample size: Sample size was estimated in PASS

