V2012 (Kayesville, UT) in order to enroll a sufficient number of obese children to detect differences in SCFA synthesis for aim 3. Based on this sample size, the number of lean children was then determined to detect differences between lean and obese (aim 1). For aim 1, given a standard deviation of 1.0 for SCFA, 100 lean children (compared to 100 obese children) will be required to detect a difference of 0.65 with 90% power at the two-sided 0.05 significance level. This sample size will also provide 80% power to detect an rsquare of 0.07 (aim 2). Statistical analyses: Analysis for Aim 1: the primary outcome will be the peak percent change from fasting in total SCFA estimated by dividing the difference between total SCFA at fasting and the peak total SCFA by the total SCFA at fasting. Total SCFA is calculated by summing the synthetic rates of the single SCFAs. Peak percent change will be compared between the lean and obese groups using a mixed model to account for the pair matching. A fixed effect will be included for group (obese/lean) and a random effect for an indicator of the matched pair. Differences in means along with 95% confidence intervals will be estimated. We will also explore between group differences in SCFA across all post-inulin time-points by estimating the area under the curve following inulin. Since the pre-intervention diet will be based on the subjects' usual intake, we will adjust for dietary intake to try to overcome the possibility that dietary patterns during the study might affect SCFA synthesis. Since the two groups will be matched by age, gender, Tanner stage and ethnicity the analyses will not need to be adjusted for these variables. Nevertheless, we will determine whether differences between lean and obese groups are modified by gender by adding an interaction of gender by group. Analysis for Aim 2: To evaluate the association between total SCFA and de novo lipogenesis, peak percent changes in de novo lipogenesis will be regressed on peak percent changes in total SCFA using a mixed model. The mixed model will include a fixed effect for peak percent total SCFA and a random effect for the matched pair indicator. To explore whether the magnitude of the associations may be dependent on other variables (such as gender), interactions between percent peak total SCFA and these variables will be included to the models in order to describe the degree of effect modification. An additional exploratory analysis using a doubly multivariate repeated measures mixed model will be evaluated to examine the correlation of total SCFA and de novo lipogenesis across all post-inulin time-points.

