
Statistical Plan for Aim 3. Justification of Sample size: In our preliminary data from obese children we observed a standard deviation for percent peak total SCFA synthesis of 1.0 and an absolute difference of 1.5% between those with the lowest and highest BMI. Given the following: 1) a power of 90%, 2) a standard deviation of 1.0, and 3) a two-sided 0.05 significance level a sample size of 21 obese children receiving both low CHO vs control diet will be required to detect a difference of 0.75 in peak total SCFA synthesis. The conservative 0.75 difference was selected based on being 50% of that estimated between the highest and lowest BMI in our preliminary work. We'll enroll 26 obese children for aim 3 to accommodate up to a 20% dropout. Statistical Analyses: The primary objective of the analysis is to demonstrate that a low CHO diet will lower SCFA synthetic rate more than control at follow-up. The percent change in peak total SCFA rate, calculated as the follow-up peak total SCFA minus the baseline peak total SCFA divided by the baseline peak total SCFA, will be compared between the low CHO period and the control period using a repeated measures mixed model. The mixed model will include fixed effects for treatment and period as well as the baseline covariates of SCFA, age, sex, pubertal stage and ethnicity. A random effect will be included for subject to allow for correlation between repeated measures. The treatment by period interaction will be evaluated and if significant ($p < 0.10$) examination of the primary aim will focus on the interventions received during the first period (i.e. to exclude the possibility of carryover). Linear contrasts and two-sided 95% confidence intervals will be estimated comparing mean percent peak total SCFA change for low CHO to control. Sex-specific effects of low CHO will be assessed by inclusion of interactions of treatment with sex. Given the assumption required for missing data, we will evaluate patterns of missing data as well as determine baseline characteristics that are predictive of dropout. If identified, these characteristics will be included as covariates in supportive sensitivity analysis.

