If Yes, please be aware of the following requirements:

A YNHH New Product/Trial Request Form must be completed via EPIC: Pull down the Tools tab in the EPIC Banner, Click on Lawson, Click on “Add new” under the New Technology Request Summary and fill out the forms requested including the “Initial Request Form,” “Clinical Evidence Summary”, and attach any other pertinent documents. Then select “save and submit” to submit your request; AND

Your request must be reviewed and approved in writing by the appropriate YNHH committee before subjects/subjects may be scheduled to receive the investigational device or investigational procedure.

2. Background Information: Provide a description of previous human use, known risks, and any other factors that might influence risks. If this is the first time this device is being used in humans, include relevant data on animal models. *Write here*

3. Source:

- Identify the source of the device to be used. *Write here*
- Is the device provided free of charge to subjects? Yes No

4. Investigational device accountability: State how the PI, or named designee, ensures that an investigational device is used only in accordance with the research protocol approved by the HIC, and maintains control of the investigational device as follows:

- a) Maintains appropriate records, including receipt of shipment, inventory at the site, dispensation or use by each participant, and final disposition and/or the return of the investigational device (or other disposal if applicable): *Write here*
- b) Documents pertinent information assigned to the investigational device (e.g., date, quantity, batch or serial number, expiration date if applicable, and unique code number): *Write here*
- c) Stores the investigational device according to the manufacturer's recommendations with respect to temperature, humidity, lighting, and other environmental considerations: *Write here*
- d) Ensures that the device is stored in a secure area with limited access in accordance with applicable regulatory requirements: *Write here*
- e) Distributes the investigational device to subjects enrolled in the IRB-approved protocol: *Write here*

SECTION III: RECRUITMENT/CONSENT AND ASSENT PROCEDURES

1. Targeted Enrollment: Give the number of subjects: 200
 - a. Targeted for enrollment at Yale for this protocol: Children and adolescents between 15 and 25 years of age.
 - b. If this is a multi-site study, give the total number of subjects targeted across all sites: NA

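### The Aim 1 inputs need 51 per group, not the 100 stated as required, and the Aim 2 R-square statement does not fit 200 subjects

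*Combined protocol and SAP*

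**What the plan says.** In the combined protocol and SAP, Section I, item 13 (Statistical Plan for aims 1 and 2), the sample size is said to have been estimated "in order to enroll a sufficient number of obese children to detect differences in SCFA synthesis for aim 3", with the lean number then set for the lean–obese comparison. For Aim 1, with a standard deviation of 1.0 and a two-sided 0.05 level, "100 lean children (compared to 100 obese children) will be required to detect a difference of 0.65 with 90% power". For Aim 2 the paragraph adds: "This sample size will also provide 80% power to detect an rsquare of 0.07 (aim 2".

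The Aim 1 analysis is a matched-pair mixed model: "A fixed effect will be included for group (obese/lean) and a random effect for an indicator of the matched pair". The Aim 2 model has one fixed effect, the peak percent change in total SCFA, with the same pair term.

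Under Aim 3 the plan needs 21 obese subjects and will "enroll 26 obese children for aim 3 to accommodate up to a 20% dropout". No dropout allowance or within-pair correlation is given for Aims 1 and 2.

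The overall target is in Section III, item 1: "Targeted Enrollment: Give the number of subjects: 200". Section I, item 12 rates the study "GREATER THAN MINIMAL RISK" overall and, for children, as "presenting a minor increment over minimal risk".

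**The concern.** The Aim 1 sentence gives every input of a standard two-group calculation, and the answer it reports is about twice what those inputs produce. The Aim 2 sentence is off by a similar factor. The sentence that traces the obese number to Aim 3 cannot account for 100, because Aim 3 enrols 26.

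Both errors run towards excess power, so the tests are not weakened. What is at stake is the justification. This paragraph is the only statistical argument for the 200 enrolled under Aim 1, where each participant has an isotope infusion and hourly blood sampling through the day. A reader weighing that burden is told that 100 per group is necessary to detect 0.65, and it is not.

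**Working it through.** **Inputs (Section I, item 13).** Aim 1: SD 1.0, difference 0.65, two-sided 0.05, power 90%, equal groups. Aim 2: R-square 0.07, power 80%, one tested predictor. Within-pair correlations, and any dropout rate for Aims 1 and 2, are my assumptions.

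**Does the plan's own method reproduce elsewhere?** Yes. Aim 3 (difference 0.75, SD 1.0, two-sided 0.05, 90% power), taken as a paired t test with SD of differences 1.0, gives 88.9% power at 20 subjects and 90.5% at 21. This matches the stated 21.

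**Aim 1, normal approximation.** n per group = 2 × (1.960 + 1.282)² × SD² / difference² = 2 × 10.51 / 0.4225 = 49.7, so 50.

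**Aim 1, noncentral t.** Noncentrality = 0.65 / √(2/n), with 2n − 2 degrees of freedom.

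| n per group | Power for 0.65 |
|---|---|
| 50 | 89.6% |
| 51 | 90.2% |
| 64 | 95.4% |
| 100 | 99.6% |

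The requirement is 51 per group. Rounding of 0.65 (0.645 to 0.655) moves it only between 52 and 50.

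**What would bring 51 up to 100?**
- *Dropout.* Aim 3's 20% gives 51 / 0.8 = 63.75, so 64 per group. Reaching 100 takes 1 − 51/100 = 49%.
- *A larger SD.* 0.65 needs 100 per group only if the SD is 1.41.
- *Pair matching.* With variance of the pair difference 2(1 − ρ)SD², a paired t test needs 52 pairs at ρ = 0, 42 at 0.2 and 27 at 0.5. Positive correlation widens the gap.
- *The Aim 3 derivation.* If the obese number were 26, even 500 lean subjects would give 89.7% power for 0.65. If it is fixed at 100, 34 lean subjects suffice (90.2%). Neither route yields 100 and 100.

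**Aim 2.** Noncentral F with 1 and N − 2 degrees of freedom and noncentrality N × 0.07/0.93 = 0.0753N, observations taken as independent.

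| N in total | Power for R-square 0.07 |
|---|---|
| 100 | 77.5% |
| 106 | 79.9% |
| 107 | 80.3% |
| 200 | 97.1% |

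The requirement is 107 in total, or 107 / 0.8 = 133.75, so 134, with 20% dropout. Rounding of 0.07 (0.065 to 0.0749) gives 115 to 99.

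**What 100 per group detects.** For Aim 1 at 90% power, 0.46 SD unpaired. With 100 complete pairs it is 0.46, 0.41 and 0.33 at ρ = 0, 0.2 and 0.5; with 80 complete pairs it is 0.52, 0.46 and 0.37. For Aim 2 at 80% power and N = 200, the R-square is 0.038.

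**The case against.** The strongest case for leaving the paragraph alone is that the surplus harms no inference and that unstated reasons could explain it.

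- *Sex-specific sizing.* The plan matches on gender and tests a gender-by-group interaction. If each group were half female, each sex would compare 50 with 50, and power for 0.65 would be 89.6%, close to the stated 90%. This is the best candidate, but the plan never says the sample was sized within sex. The interaction test itself would have only about 63% power for 0.65.
- *Loss of whole pairs.* If only complete pairs counted, independent 30% dropout (the Background cites attrition near that level at 12 months in child weight-loss programs) would leave 0.7² × 100 = 49 pairs, with 88% power at zero correlation. But the planned mixed model keeps unpaired subjects, positive correlation lowers the need, and the Aim 1 outcome comes from a short test, not a year-long program. The point does show that 20% individual dropout would leave about 64 complete pairs (0.8² × 100), so the 80-pair figures above must be read as 80 pairs retained.
- *Aim 2.* Seven jointly tested predictors would bring power at 200 down to 80.5%, but the model has one. The 80% might be meant as a floor, and the 200 is inferred from the reference to the same sample size. This makes Aim 2 the less clear-cut of the two mismatches.
- *Other aims.* Aims 3, 5 and 6 are sized separately, but the 100 obese and 100 lean are enrolled under Aim 1, so those calculations do not justify 200.

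The absence of inferential harm stands. None of the explanations is written in the plan, and if one is the true reason, the paragraph still has to say so.

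**Conclusion.** The concern holds. On the stated inputs, Aim 1 needs 51 per group against 100 stated, and power at 100 is 99.6%, not 90%. Aim 2 needs about 107 in total against 200, and power at 200 is 97%, not 80%. The Aim 3 sentence does not explain 100 obese subjects. The Aim 1 figure assumes an unpaired t test and complete data; matching with positive correlation would lower it. The Aim 2 figure assumes one predictor and independent observations. The study is not underpowered for the stated effects, and 200 may be defensible for a reason not given. The plan should be corrected because the number enrolled rests on a statement that its own inputs contradict.

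**What to change.** Rewrite the sample-size paragraph so that number, effect size and assumptions agree, and state the attrition and within-pair correlation assumed for Aims 1 and 2. Two routes are open:

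1. Keep 0.65 and R-square 0.07, state the sizes they need (51 per group; about 107 in total, before dropout), and give the actual reason for enrolling 200.
2. Name the effect the study is meant to detect, say why it matters, and show that 100 per group fits it. For independent, complete observations that is about 0.46 SD at 90% power for Aim 1 and an R-square of about 0.038 at 80% power for Aim 2.

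In either case, correct or remove the sentence that derives the obese number from Aim 3. The cost is wording only, with no added participants or procedures.

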Microbiota dysbiosis may influence the development of obesity through several mechanisms, including the production of bio-active metabolites^{5,28}, in particular, the short chain fatty acids (SCFA) (acetate, butyrate and propionate)²⁹. The SCFA are among the most abundant microbiota-derived metabolites and are produced through the fermentation of dietary carbohydrates not digested by the host. Direct evidence of the role of gut microbiota in energy harvest and fat deposition comes from germ-free rats, which have reduced intestinal levels of SCFA³⁰, and twice as much urinary and fecal excretion of calories as that of conventional ones fed the same polysaccharide-rich diet³¹. Microbial energy harvest in obesity has been investigated in conventional genetically obese ob/ob mice, revealing increased amounts of SCFA in their caecum and reduced energy content in their feces compared to their lean littermates³². In vitro and animal studies suggest that, once produced, SCFA may enter the circulation and may be utilized for de novo lipid or glucose synthesis^{33,34}. While the role of gut microbiota in promoting energy harvest has been shown in animal studies, the only evidence in humans derives from indirect investigations. For instance, people who are obese have higher levels of ethanol in their breath than lean³⁵ and show greater amounts of fecal SCFA³⁶, which suggests altered fermentation and increased microbial energy harvest.

Mechanisms by which the SCFA can modulate the human metabolism.

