
When possible, the MRI scan will be on the same day as the OGTT as noted above, however it can be scheduled on a different day (either prior to or following completion of OGTT) based on ease of scheduling for the patient.

Aim 1: Determine whether the gut microbiota of obese adolescents have greater ability to ferment carbohydrates

(CHO) and synthesize SCFA compared to the microbiota of lean subjects, therefore obtaining a higher metabolizable energy yield from an equal amount of dietary CHO. *Hypothesis: For an equal amount of dietary CHO, obese youth will synthesize SCFA at higher rates than lean youth.*

All subjects will be instructed about the benefit of a healthy diet and will meet with the dietitian who will advise on healthy feeding behavior and lifestyle and will be given the option of enrolling, free of charge, in the Yale Pediatric Weight Management Program called “Bright Bodies.” The program includes the following components: exercise, nutrition education, behavior modification, and psychosocial support.

We will enroll an equal number of obese (100) and lean (100). Lean adolescents will be recruited if at risk of developing obesity, prediabetes or diabetes due to their family history. The dietitian will instruct the subjects to follow a 3-day pre-intervention meal plan to ensure standardized calories and macronutrients intake up to the day of investigation in amounts to maintain weight in both groups. The pre-intervention diet will be based on the subjects’ age, weight and usual intake. The subjects will be admitted at the Hospital Research Unit (HRU) of the

[figure not shown]
Yale New Haven Hospital at 7.00 AM. To determine SCFA synthetic rates we will give orally 20g of lactulose, an oligosaccharide naturally present in nature that is extracted from chicory. To account for hepatic uptake, isotope exchange in the TCA cycle in the liver

and endogenous production by the liver, deuterated-SCFA will be infused from 7.30 AM, this will allow us to reach the quasi steady state for 2H-SCFA after ~1 hour. We will infuse 0.7 micromol/kg/min of labeled acetate after a labeled acetate priming dose of 1 mg/Kg. To assess SCFA synthesis blood samples will be collected every hour until 6.00 pm for a total of 150 ml (Figure 1). The subjects will be allowed to drink during the study, a meal will be served at the end of the study.

[figure not shown]

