We will also collect the breath hourly hydrogen breath test during the study to assess colonic fermentation by measuring hydrogen in the breath. Subjects blow into a small box to collect the breath. There are no risks related to this test.

Rationale for using lactulose as substrate to measure SCFA synthesis. In order to study the ability of the gut microbiota to ferment carbohydrates, we have chosen lactulose because the SCFA synthesis and kinetics arising from lactulose ingestion has been widely studied and is well known. Due to the structural conformation of its linkages, lactulose resists hydrolysis in the human small intestine and is almost completely fermented by the colonic microbiota. Lactulose has low osmotic activity, however it may cause uncomfortable bowel movements, flatulence, loose stools, bloating, cramps, and diarrhea.

Aim 1 Follow-up: After the completion of Aim 1, participants will be invited back for a one-year follow-up to measure height, weight, body mass composition with the Tanita scale, and to collect a 3-day food log. This follow-up is to assess if acetate production predicts change in BMI and body composition one year post study.

Aim 2: Determine whether the SCFA synthetic rates modulate hepatic de novo lipogenesis. Hypothesis: High rates of SCFA synthesis enhance hepatic de novo lipogenesis. Subjects will assume 3ml/ Kg of body water of D2O in three doses *per os* (at 7:00 PM, 10:00 PM and 3:00 AM) the night before the study. At the test day at 7:30 AM they will consume 2g of ¹³C Inulin, 13g of unlabeled inulin. Blood draws will be taken every hour until 8:00 PM. The total blood to be drawn is about 150 ml. The subjects will be allowed to drink during the study, a meal will be served at the end of the study.

[figure not shown]
We will also collect the breath hourly hydrogen breath test during the study to assess colonic fermentation by measuring hydrogen in the breath. Subjects blow into a small box to collect the breath. There are no risks related to this test.

Aim 3: Test the effect of an isocaloric low carbohydrate (CHO) diet on the bacterial synthesis of SCFA.

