To assess how COVID-19 lockdown has changed the dietary habits of participants enrolled in this study. In order to collect this information, we will ask for the participant to complete an online 3-day food record. This part of the study is non-invasive and there will be no in-person contact.

Aim 5 – Exploratory

To assess whether the colonic fermentation modulates gluconeogenesis. Hypothesis: Glucose fermentation induced by lactulose is associated with a drop in gluconeogenesis. Subjects will assume 3ml/ Kg of body water of D2O in three doses *per os* the night before the study and at 7:30 AM they will consume 20g of lactulose. Blood draws will be taken every hour until 8:00 PM. The total blood to be drawn is about 150 ml. The subjects will be allowed to drink during the study, a meal will be served at the end of the study.

We will also collect the breath hourly hydrogen breath test during the study to assess colonic fermentation by measuring hydrogen in the breath. Subjects blow into a small box to collect the breath. There are no risks related to this test.

Aim 6 - Measurement of TCA cycle in vivo in the brain and in the liver by using Deuterium metabolic imaging.

Deuterium metabolic imaging (DMI) is a simple MR-based technique to map metabolism with high temporal and/or spatial resolution. The metabolic fate of deuterated substrates, including glucose and acetate, can be monitored with deuterium MR methods. Recent preliminary data obtained with this protocol suggest that youth with obesity have higher TCA cycle compounds in plasma than lean. This is probably due to an increased metabolic rate related to insulin resistance. To determine if changes observed in plasma mirror metabolic changes in the tissue (brain and liver), we will use a technique that combines stable isotopes and MRI. To measure TCA cycle in the brain we will use 6,6-2H₂-glucose, a compound that has been used for many years in clamp studies, while to measure TCA cycle in the liver we will use D3-Acetate, the compound that we are currently using to measure acetate production (Aim 1 and 3).

TCA cycle measurement in the brain.

To measure TCA cycle measurement in the brain we will infuse 6,6-2H₂-glucose for 2 hours and we will detect the changes in TCA derived compounds in the brain during the infusion. A total of 50 ml of blood will be obtained during this study.

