The labeled glucose is prepared by the Investigational Drug Service of the Yale Pharmacy, as a solution of 20% (w/v) in water. The labeled glucose is infused following a protocol used for decades in the Yale Magnetic Resonance Research Center (MRRC), consisting of a ramp phase followed by a plateau phase. The amount of glucose infused is 0.75g/kg body weight (BW); the volume of glucose solution infused over a 120 min study is 3.6 ml/kg BW.

TCA cycle measurement in the liver.

To measure TCA cycle measurement in the liver we will infuse d3-acetate for 2 hours and we will detect the changes in TCA derived compounds in the liver during the infusion. A total of 50 ml of blood will be obtained during this study.

The labeled acetate is prepared by the Investigational Drug Service of the Yale Pharmacy, as a solution of 350 mM 2H-labeled sodium-acetate in water. The labeled acetate is infused following a protocol used for decades in the Yale MRRC, consisting of a ramp phase followed by a plateau phase. The amount of acetate infused is 0.73g/kg body weight (BW); the volume of acetate solution infused over a 120 min study is 14.2 ml/kg BW.

Calendar of activities for each aim (visits, frequency, assessments, blood draw collection, week number).

Visit number	Frequency	Assessment	Amount of blood to be collected	Week number
AIM 1				
1	once	OGTT	120	1
2	once	Acetate synthesis	94	2
AIM 2				
1	once	DNL assessment	150	3
AIM 3				
1	once	Acetate synthesis	94	4
2	once	Acetate synthesis	94	5
3	once	Acetate synthesis	94	6
4	once	Acetate synthesis	94	7
AIM 4				
1	once	One year follow-up	0	8
AIM 5				
1	once	gluconeogenesis	150	9
AIM 6				
1	once	MRI/Infusion - Brain	50	10
2	once	MRI/Infusion - Liver	50	11

Each visit is one day. If a subject is recruited for more than one aims, then at least 12 weeks will be allowed between the visits

5. Genetic Testing

The genetics portion of the study is optional. Subjects who do not wish to have additional blood drawn for genetic analysis may still have the OGTT. We may wish to contact family members of the subject for the genetic study as well. However, no family member will be contacted without the permission of the index subject, and

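### Aims 1 and 3: the primary outcome sums several SCFA synthetic rates, but the visits as described measure acetate, and no procedure is given for propionate or butyrate

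*Combined protocol and SAP*

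**What the plan says.** **Outcome.** In Section I, item 13 (Statistical Considerations), for Aim 1 "the primary outcome will be the peak percent change from fasting in total SCFA". The same paragraph adds: "Total SCFA is calculated by summing the synthetic rates of the single SCFAs". The Aim 3 plan compares diets on the percent change in peak total SCFA rate. In Aim 2, total SCFA is the explanatory variable and de novo lipogenesis is the outcome. The Background says which acids are meant: "the short chain fatty acids (SCFA) (acetate, butyrate and propionate".

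**Procedure.** The Research Plan for Aim 1 opens in general terms: "deuterated-SCFA will be infused from 7.30 AM, this will allow us to reach the quasi steady state for 2H-SCFA after ~1 hour". The only prime and rate it then gives are for acetate: "We will infuse 0.7 micromol/kg/min of labeled acetate after a labeled acetate priming dose of 1 mg/Kg". Aim 3 refers back to the Aim 1 procedure. Aim 6 describes D3-acetate as "the compound that we are currently using to measure acetate production (Aim 1 and 3". The Aim 1 follow-up is worded in the same way: "This follow-up is to assess if acetate production predicts change in BMI and body composition one year post study". In the calendar of activities, the second Aim 1 visit and all four Aim 3 visits are listed as "Acetate synthesis".

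**Other mentions.** The isotope list in Section II has one joint entry for deuterated SCFA and labelled acetate, and names no propionate or butyrate label. Section IV says that SCFA will be measured in plasma, without naming the acids or the method.

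**The concern.** A sum of synthetic rates needs a rate for each term. The Aim 1 text explains that the infused tracer is there to allow for hepatic uptake, isotope exchange in the liver and endogenous production. On the plan's own reasoning, then, a plasma level of propionate or butyrate does not stand in for a synthetic rate.

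Two things are at stake. The first is the claim: if acetate is what is measured, a conclusion about total SCFA synthesis goes beyond the data. The second is pre-specification. With the definition and the procedures at odds, an analyst could report acetate, a total, or some mixture, and could choose after seeing the data. The planning SD and detectable differences are also stated for SCFA or total SCFA, so they do not carry over to acetate without justification.

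**Working it through.** No stated figure has to be reproduced for the mismatch itself. The check is to set the definition beside each place that describes the measurement.

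| Place | What it describes |
|---|---|
| Item 13, Aim 1 | sum of the single SCFA rates |
| Item 13, Aim 3 | percent change in peak total SCFA rate |
| Research Plan, Aim 1, opening | deuterated SCFA, acids not listed |
| Research Plan, Aim 1, prime and infusion | acetate only |
| Research Plan, Aim 3 | as in Aim 1 |
| Aim 1 follow-up | acetate production |
| Research Plan, Aim 6, on Aims 1 and 3 | acetate production by D3-acetate |
| Calendar, 1 + 4 = 5 visits | acetate synthesis |
| Section II isotope list | deuterated SCFA and labelled acetate, one entry |
| Section IV | SCFA in plasma, method not stated |

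Every place that is specific says acetate. The places that say SCFA name no acid and give no method. Of the three terms in the sum, one has a described tracer and two do not. The planned measurements affected number 200 × 1 + 26 × 4 = 304 visits.

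**Why a total and one component are not interchangeable.** Let s be acetate's share of the fasting total, A the percent change in acetate and O the percent change in the rest. At a given time the percent change in the total is T = s·A + (1 − s)·O. The documents give no shares, so the following is an assumption: s between 0.5 and 0.9, equal in both groups, with O = 0.

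- Aim 1: a difference of 0.65 in acetate becomes 0.65 × 0.5 = 0.325 to 0.65 × 0.9 = 0.585 in the total.
- Aim 3, with s taken at the baseline peak: 0.75 becomes 0.375 to 0.675.

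Under these assumptions the SD shrinks by the same factor s, so this alone does not lower power. It shows that a planning value for one quantity is not a planning value for the other. If O is not zero, the two may also peak at different times.

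**The planning figures.** For Aim 3, a paired t test with difference 0.75, SD 1.0 (read as the SD of the within-subject difference) and n = 21 gives power 90.45%, so the stated 21 reproduces. For Aim 1, n per group = 2 × (1.960 + 1.282)² × 1.0² / 0.65² = 49.7, that is 50. The stated 100 per group does not reproduce at 90% power, but that is a separate point which does not bear on this one.

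**Sensitivity to an acetate SD.** None is given. Keep the difference at 0.65 with 100 per group and take power = Φ(0.65 / (SD × √(2/100)) − 1.96):

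| Assumed SD | Power |
|---|---|
| 0.75 | over 99.9% |
| 1.0 | 99.6% |
| 1.25 | 95.7% |
| 1.5 | 86.5% |
| 2.0 | 63.2% |

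**The case against.** The strongest reply is that the Aim 1 text does speak of deuterated SCFA and a steady state for them, and that the Section II list repeats the term. Only the dosing detail is confined to acetate. The figures for these visits are missing from the text available and might name further tracers. The sponsor also reports an SD of 1.0 for percent peak total SCFA synthesis from preliminary data in obese children, so it has evidently calculated such a quantity before.

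These points rule out three stronger readings that a reader might reach.

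- **That the outcome cannot be computed, or that no corrected propionate or butyrate rate can exist.** The documents do not say so. They give no procedure, which is a narrower statement.
- **That the problem runs identically through Aims 1 to 3.** In Aim 2, total SCFA is the predictor. The visit uses oral 13C-inulin and D2O, with no SCFA tracer infusion described. Its gap is a different one: how an SCFA rate is obtained from that visit.
- **That the plan would add one corrected rate to two uncorrected concentrations.** Nothing in the text proposes this.

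It is also fair to say that making acetate the outcome is more than a change of words, since the acetate SD and effect size would need their own basis. Data have already been gathered under this protocol: Aim 6 cites preliminary results from it, and the request for a HIPAA waiver refers to recruitment over past years.

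The contradiction remains. No section names a propionate or butyrate tracer or a method for their rates, and four separate places describe the Aim 1 or Aim 3 measurement as acetate.

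**Conclusion.** The concern holds for Aims 1 and 3 as an internal inconsistency: the primary outcome is defined on a sum of SCFA synthetic rates, while the described measurement is acetate. It affects the primary outcome of all 200 Aim 1 subjects and of all 26 Aim 3 subjects at each of their four SCFA visits. The direction and size of any distortion cannot be stated, because neither the share of each acid nor an acetate SD is given; the ranges shown above are illustrations only. The verdict rests on the text as available, and a missing figure could supply the tracer list. Even then, the written sections would disagree and would need to be aligned. Aim 2 has a related but separate gap in the definition of its predictor.

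**What to change.** Reconcile the Aim 1 and Aim 6 parts of the Research Plan, the calendar of activities, the Aim 1 and Aim 3 parts of item 13, and the isotope list in Section II. Do this before the outcome data are analysed, and record which data had been seen by then.

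- **If acetate is the only SCFA traced:** define the primary outcome of Aims 1 and 3 as the acetate synthetic rate, in the same percent-change forms. Limit the conclusions to acetate, and report propionate and butyrate only as secondary concentrations. Re-justify the SD of 1.0 and the differences of 0.65 and 0.75 for acetate.
- **If other labelled SCFAs are infused:** name them wherever the tracer is described and state how each synthetic rate is obtained. The sum can then stand. The choice of tracers is the sponsor's.
- **Aim 2, in either case:** state which SCFA measure from that visit is the predictor and how it is calculated.

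The acetate route costs a narrower claim and a revised sample-size justification, with no new samples. The other route costs a fuller description of the method.
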